9.10. Sample Handling

The biological sample (e.g. finger prick blood test, nasal swab) required for the CA-ARTI-Dx will be taken in patients randomised to care with the addition of that CA-ARTI-Dx. The samples will be handled and processed according to the kit instructions for the CA-ARTI-DX and any leftover sample will be disposed of as per local procedures for clinical waste. No other samples will be taken.

If the responsible clinician considers that a microbiological sample is necessary for the purposes of routine care, they will need to obtain an additional sample according to their routine processes.

Participants included in the LTCF setting may be invited to participate in a sampling sub-study as described in appendix J.

9.11. Nested Process Evaluation

A mixed-methods process evaluation will be nested within the trial. The process evaluation will capture data to understand how the intervention is used and viewed by clinicians and patients in order to explain how clinicians and patients adopt CA-ARTI-Dx in community care. Not all countries included in the PRUDENCE study will participate in the Nested Process Evaluation Interviews. See appendix G for the current list of participating countries.

Interviews:

4-5 countries from the 12 that participate in the trial will be used as case studies that reflect diversity in relevant factors such as healthcare system, community care settings, income, geographic location in Europe and antibiotic use.

We will carry out interviews (telephone, online (e.g. using Microsoft Teams or face to face as appropriate) with patients participating in the trial throughout the recruiting period. All patients will be eligible to take part in an interview unless they do not have capacity. Interviews will capture experiences of and satisfaction with care when a CA-ARTI-Dx is used and subsequent views and experiences of management of symptoms (including antibiotic use). Some patients recruited to intervention arms in the trial (approximately 8-10 per country) will be purposively sampled across recruiting periods to give a total of 32-50 interviews. We will seek to obtain variation in age, symptom presentation, type of CA-ARTI-Dx carried out and whether an antibiotic is prescribed. Parents/carers of child patients under 12 will be invited to interviews. Patients aged 12 years and older will be invited to interviews, with parents able to sit in on interviews with children under 16 where desired. Patients will be provided with Patient Invitation Letter and Patient PIL. We will obtain written or oral consent prior to an interview. A password protected copy of the consent will be emailed to participants.

In addition, we will conduct (telephone, online (e.g. using [name]) or face to face as appropriate) interviews with healthcare professionals to capture experiences using CA-ARTI-Dx in daily clinical practice, and identify any additions and improvements required when rolling out CA-ARTI-Dx and any training materials during the trial in order to meet clinicians' and patients' needs and support use. Any health professionals supporting PRUDENCE will be eligible to take part and CIs at each site will identify and invite professionals. Different health professionals (approximately 7 per country, each representing a participating practice/faculty) will be purposively sampled across each of the recruiting periods to give a total of 28-35 interviews. We will seek to obtain variation in professional role, practice setting, and experience. Healthcare professionals will be provided with Clinician Invitation Letter and Clinician PIL. We will obtain written or oral consent prior to an interview. A password protected copy of the consent will be emailed to participants.

Semi-structured topic guides will be informed by existing literature and theory, including the Theoretical Domains Framework and the Common Sense Model, to ensure that questions elicit likely key determinants of behaviour, and Normalization Process Theory to identify how POCT diagnostics could be embedded in routine practice. Data will be analysed using thematic and framework analysis (1, 2).

Surveys:

Surveys will assess the views of clinicians and patients on the use of CA-ARTI-Dx in ARTI consultations, examine how CA-ARTI-Dx are implemented and experienced.

Patient surveys will be included in the participant diary on Day 1 and in the follow-up telephone call at Day 28 (as described above). Surveys will include brief statements measuring patient satisfaction with the consultation, beliefs about the necessity of antibiotics for respiratory symptoms and future behavioural intentions to manage symptoms and (re)consult for future illness. Patient surveys will be included for all participants in all trial sites.

Clinician surveys will be sent electronically to all participating clinicians at each site as sites are recruited, prior to patient recruitment starting at that site. Clinicians will be asked to complete the survey at two time points: prior to patient recruitment at their site and on completion of patient recruitment at their site. Additional timepoints may be added if sites adopt a new CA-ARTI-Dx during the trial. Surveys will

include brief statements measuring attitudes about use of CA-ARTI-Dx, implementation of CA-ARTI-Dx and future behavioural intentions to use CA-ARTI-Dx. Clinician surveys will be conducted in all participating countries in the trial.

9.12. Early Discontinuation/Withdrawal of Participants

Each participant has the right to withdraw from the study at any time. In addition, the Investigator may discontinue a participant from the study at any time if the Investigator considers it necessary for any reason including:

- BD Veritor SARS-CoV-2 positive test result (discontinued after baseline visit prior to randomisation)
- Ineligibility (either arising during the study or retrospectively having been overlooked at screening)
- Withdrawal of consent

The reason for withdrawal will be recorded in the CRF. Data that has already been collected about the participant will be kept.

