8.3. Exclusion Criteria

- Patients with only nasal, ear or rhinosinusitis symptoms
- Patients who have tested positive to SARS-CoV-2 within 28 days of onset of symptoms
- Patients with any serious condition associated with immunocompromised (long term oral steroids or immunosuppressants, terminal cancer)
- Patients for whom the clinician decides on immediate hospital admission
- Patients who will not be able to participate in the study because they do not understand the local language; are terminally ill; have a serious psychiatric disorder; or judgement of the recruiting clinician deems ineligible.

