9.6. Blinding and code-breaking

PRUDENCE will be an open trial. The participant and the recruiting clinician will know the participant's allocation. Therefore, no unblinding or code breaking is required in the event of a relevant emergency.

The trial team and recruiting clinicians will be blind to emerging results. During the course of the trial, only those on the Data Monitoring Committee will have access to the unblinded data as part of the interim analysis.

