11.7. Adaptive Arm Stopping and Addition of New Arms

The trial will continue through two winter seasons of CA-ARTI (typically October to May), and each winter season will encompass a shorter influenza season (length varies by year). A single interim analysis will be conducted in between winter seasons, in which both of the co-primary endpoints are evaluated for each of the CA-ARTI-Dx. If early success or futility is determined for either CA-ARTI-Dx relative to usual care, a new CA-ARTI-Dx will replace the given CA-ARTI-Dx in the second winter season. Otherwise the given CA-ARTI-Dx will be continued in the second CA-ARTI season. The co-primary endpoints and primary analyses will remain the same for any newly introduced CA-ARTI-Dx arms. Decision rules for claiming superiority of a given CA-ARTI-Dx upon conclusion of either winter season will be calibrated to control the overall Type I error for each CA-ARTI-Dx at the approximate one-sided 0.025 level. These thresholds will be pre-specified. Any additional CA-ARTI-Dx introduced in the second winter season will require a statistical Appendix/Addendum to update the SAP.

11.8. **Analysis populations**

The primary analyses will include all participants in the intention to treat (ITT) population, i.e. all participants randomized and analysed in their respective randomized assignment. Additional populations

will be described in the SAP; this includes all participants who underwent the intervention (a safety population); all eligible participants (a per protocol analysis); and an "as treated" population.

11.9. Procedure for Accounting for Missing, Unused, and Spurious Data.

For a given endpoint, the primary analyses will be conducted using complete cases, i.e. ignoring patients with missing endpoints. Sensitivity analyses will be conducted exploring the impact of missing data and any biases that may be present.

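### Section 9.12 lets an investigator who knows the allocation take a randomised participant out of the study for ineligibility, and the complete-case rule can then drop that participant from the ITT primary analysis

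*Protocol*

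**What the plan says.** Section 9.12 gives a wide discretion: "the Investigator may discontinue a participant from the study at any time if the Investigator considers it necessary for any reason including". One listed ground is "Ineligibility (either arising during the study or retrospectively having been overlooked at screening". The SARS-CoV-2 item in the same list is expressly placed before randomisation; the ineligibility item is not. On data, the section says only this: "Data that has already been collected about the participant will be kept".

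Section 9.6 states "PRUDENCE will be an open trial" and adds: "The participant and the recruiting clinician will know the participant's allocation".

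Section 11.8 defines the primary (ITT) population as "all participants randomized and analysed in their respective randomized assignment", and places the set of eligible participants in a separate per-protocol analysis. Section 11.9 then says: "For a given endpoint, the primary analyses will be conducted using complete cases, i.e. ignoring patients with missing endpoints". It also plans sensitivity analyses for missing data.

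Both co-primary endpoints depend on the daily diary or Day 14 call and on the Day 28 call (sections 6 and 9.9).

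**The concern.** What 9.12 ends is participation in the study, not only use of the test strategy, and no sentence says that the diary and calls continue. The protocol shows elsewhere what ended participation can mean. Under 9.4, a participant who is SARS-CoV-2 positive at baseline has no further trial procedures, and under 9.8 that participant is not given the diary instructions. A site could reasonably treat a randomised participant found ineligible in the same way.

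Ineligibility that surfaces after randomisation is foreseeable. Overlooked criteria come to light in any trial. One exclusion in 8.3, "Patients who have tested positive to SARS-CoV-2 within 28 days of onset of symptoms", could also be met later: patients with symptoms for more than 5 days are not tested at baseline (9.4), Appendix C treats a negative result as presumptive, and the follow-up calls ask about COVID-19 testing (9.9).

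If follow-up stops before an endpoint is known, a person who knows the allocation has decided who contributes an outcome. Time to return to usual activities is the endpoint that protects against harm from withholding antibiotics, and it is tested for non-inferiority. Selective loss of slow recoverers from the test arm would make that arm look better than it is. The rule governs conduct, so an SAP cannot fully repair it: outcomes that were never collected cannot be recovered at analysis.

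**Working it through.** **1. When a discontinued participant leaves the primary analysis**

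- *Prescribing, prescription at baseline.* The outcome is a known yes (section 9.8, part 2 of the baseline form) and the participant stays.
- *Prescribing, no prescription yet, discontinued before Day 28.* The outcome may be treated as missing. Loss then depends on the outcome itself.
- *Recovery, already reported.* The outcome is complete and the participant stays.
- *Recovery, not yet reported.* The outcome is either missing (dropped under 11.9) or censored in the piecewise exponential model of 11.5. The protocol does not say which.

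**2. The plan's own figures (Appendix F)**

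Inputs: 1250 per season, half cough and half sore throat, half in flu season, 5% missing. Each of four strata has 1250/4 = 312.5.

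- CRP comparison per arm: (312.5/3 + 312.5/2) × 0.95 = 247.4 (stated 247).
- Power = Φ(√D × |ln 0.80|/2 − 1.96), with D = 2n events. For n = 247, 69.8% (stated 69%). For n = 494 over two seasons, 93.9% (stated 93%).

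The figures reproduce. Loss of numbers alone matters little: 10% missing instead of 5% gives 234 per arm and 67.5% (one season) or 92.7% (two seasons). The issue is bias.

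**3. Illustration for recovery**

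From the protocol: control mean 4 days, margin 1 day (hazard ratio 0.80), one-sided 0.025, 494 per arm for CRP over two seasons. Assumed, because the protocol gives no figure: a true delay exactly at the margin (5 versus 4 days), a removed share q, a mean of 14 days to recovery in those removed, and total loss of their recovery data.

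The apparent mean after removal is (m − 14q)/(1 − q), with m = 5 in the test arm. Control stays at 4, or becomes (4 − 14q)/(1 − q) if removal is equal.

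- Method A (difference in means): Φ((1 − diff)/SE − 1.96), SE = √(mean_T²/494 + mean_C²/494).
- Method B (log hazard ratio): Φ(ln[(4/mean_T)/0.80]/√(1/(494(1 − q)) + 1/494) − 1.96).

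For q = 2%, test arm only: mean_T = (5 − 0.28)/0.98 = 4.82 and diff = 0.82.

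- A: SE = √((4.816² + 16)/494) = 0.282, so Φ(0.652 − 1.96) = 9.5%.
- B: Φ(0.0374/0.0640 − 1.96) = 8.5%.

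| q | Apparent delay, test arm only | False NI, A | False NI, B | Apparent delay, both arms | False NI, A, both arms |
|---|---|---|---|---|---|
| 0 | 1.00 | 2.5% | 2.5% | 1.00 | 2.5% |
| 2% | 0.82 | 9.5% | 8.5% | 1.02 | 2.1% |
| 5% | 0.53 | 41% | 33.9% | 1.05 | 1.5% |

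With equal removal the apparent delay is 1/(1 − q), which is above the true delay, so the error rate falls.

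Varying the assumed mean from 10 to 20 days (method B, test arm only) gives 3.6–7.0% for q = 1%, 5.1–16.6% for 2% and 13.1–76.0% for 5%.

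**4. Illustration for prescribing**

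With 90% prescribed in both arms, losing 2% of the test arm, all of them unprescribed, gives 0.90/0.98 = 91.8%. That is 1.8 points against the test and small beside the 15-point target.

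**The case against.** A reader might infer that everyone discontinued for ineligibility disappears and that the ITT label is empty. The documents do not support that. Section 11.8 takes all randomised participants and uses eligibility only for the per-protocol set. Section 11.9 drops people only where the endpoint in question is missing, collected data are kept, and missing-data sensitivity analyses are planned. The time-to-event model could censor rather than drop, and the SAP may say so. All of this stands. It shows that removal is possible rather than certain. Censoring linked to slow recovery would still be informative.

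A reader might also infer that worsening patients will be taken out. Worsening is not an exclusion criterion. Hospitalisation and pneumonia are secondary outcomes, serious adverse events are recorded for 28 days, and 9.13 ends the trial when enrolled patients have completed 28-day follow-up. The intention appears to be to follow such patients.

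The route to allocation-aware removal is also narrow. There is no research follow-up visit, and outcomes come from diaries and from calls by the trial team. A positive SARS-CoV-2 test reported in a call arrives together with recovery and antibiotic data, and the criterion in 8.3 reads most naturally as a screening rule. This lowers the likely frequency, but 9.12 still permits the removal.

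Finally, the larger error rates need one-arm removal, a 14-day mean, complete data loss and a true delay at the margin. The 494 per arm is already net of 5% missing. That criticism is fair, and the figures serve only as an illustration.

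**Conclusion.** The concern holds in a limited form. Section 9.12 permits an investigator who knows the allocation to discontinue a randomised participant for ineligibility, and nothing in the protocol requires follow-up to continue. Where an endpoint is not yet known, 11.9 can then drop that participant from an analysis defined on all randomised.

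The size and direction of any bias cannot be established from the protocol. Losing 2% of slow recoverers from the test arm alone would raise false non-inferiority from 2.5% to about 9–10% under the stated assumptions; equal loss in both arms would not raise it. It would be wrong to conclude that the primary analysis is biased towards non-inferiority. The supported conclusion is that the wording leaves an avoidable opening, which sits badly with the ITT and per-protocol definitions in 11.8. It is a cheap improvement, not a demonstrated failure of the design.

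**What to change.** In 9.12:

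- Limit discontinuation from the study for ineligibility to the period before randomisation.
- State that ineligibility found or arising after randomisation does not end follow-up: the diary and the Day 14 and Day 28 calls continue unless the participant withdraws consent to data collection.
- State that the participant remains in the ITT analysis, with ineligibility handled only in the per-protocol set of 11.8.

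The cost is a wording amendment and a small amount of extra follow-up using procedures already in place. The sample size and the model do not change.

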9.13. Definition of End of Study

The trial will end when all patients enrolled into the study have completed the 28 day follow-up and all subsequent data collection is complete.

10. SAFETY REPORTING

All CA-ARTI-Dx tests being evaluated in this study are CE-marked and being used within the scope of their intended use. As a result of this no adverse events will be recorded in this study. All Serious Adverse Events (SAEs) occurring during the 28 days participants are enrolled on the trial will be recorded as detailed in Section 10.2 Reporting Procedures for Serious Adverse Events.

10.1. Definition of Serious Adverse Events

A serious adverse event is any untoward medical occurrence that:

- · results in death
- is life-threatening
- requires inpatient hospitalisation or prolongation of existing hospitalisation
- results in persistent or significant disability/incapacity
- consists of a congenital anomaly or birth defect.

Other 'important medical events' may also be considered a serious adverse event when, based upon appropriate medical judgement, the event may jeopardise the participant and may require medical or surgical intervention to prevent one of the outcomes listed above.

NOTE: The term "life-threatening" in the definition of "serious" refers to an event in which the participant was at risk of death at the time of the event; it does not refer to an event which hypothetically might have caused death if it were more severe.

10.2. Reporting Procedures for Serious Adverse Events

All SAEs must be reported on the study SAE Report Form by the person who has discovered the SAE or nominated delegate, either in paper form or through the study database to the local network coordinator and the University of Oxford PC-CTU within 24 hours of the site study team becoming aware of the event. The University of Oxford PC-CTU Project Manager or delegate will perform an initial check of the report, request any additional information, and ensure it is reviewed by the CI or other delegated personnel for relatedness and expectedness. Additional and further requested information (follow-up or corrections to the original case) will be detailed on a new SAE Report Form and emailed to the sponsor or delegate. If the event has not resolved, at the 28 day time point the SAE will be reviewed again to see if resolution has occurred. If the event is considered 'resolved' or 'resolving' no further follow up is required. If not the event must be followed up until such a time point.

SAEs will be reviewed at each Data Monitoring Committee meeting.

A serious adverse event (SAE) occurring to a participant should be reported to the REC that gave a favourable opinion of the study where in the opinion of the Chief Investigator the event was 'related' (resulted from administration of any of the research procedures) and 'unexpected' in relation to those procedures. Reports of related and unexpected SAEs should be submitted within 15 working days of the Chief Investigator becoming aware of the event, using the HRA report of serious adverse event form (in the UK).

11. STATISTICS AND ANALYSES

11.1. Statistical Analysis Plan (SAP)

The statistical aspects of the study are summarised here with details fully described in a statistical analysis plan (SAP) that will be available from the time that the first participant is recruited. The SAP will be finalised before the interim analysis scheduled upon completion of the first study period evaluating the initial CA-ARTI-DX tests. This will allow the possibility of additional CA-ARTI-Dx to be evaluated in the second study period (replacing either one or all of the initial CA-ARTI-Dx), pending results of the scheduled interim analysis.

11.2. Randomization

Participants will be randomized to one of the CA-ART-Dx tests with usual care or usual care (see appendix B for a flow chart/algorithm of the current process). Randomisation stratification for the current CA-ARTI-Dx being evaluated are outlined in appendix F.

11.3. Co-Primary Endpoints

The study has two co-primary endpoints:

- 1) Whether a participant is prescribed at least one antibiotic course (of any dose or duration) over 28 days from inclusion (yes/no)
- 2) Time to return to usual daily activities (in days)

11.4. Primary Hypotheses

The study will evaluate the following hypotheses for each CA-ARTI-Dx evaluated:

- 1) CA-ARTI-Dx with usual care use is superior to usual care, as demonstrated by the following two criteria:
 - a. The proportion of participants prescribed at least one antibiotic course is lower for the CA_ARTI-Dx arm relative to the usual care arm
 - b. The mean time to return to usual daily activities is no greater than 1 additional day for the CA-ARTI-DX arm relative to the usual care arm

11.5. Primary Analyses

Analyses will be conducted separately for comparing each CA-ARTI-Dx test versus usual care.

For each CA-ARTI-Dx, the first co-primary endpoint (prescribing of antibiotics) will be analysed with a logistic regression model on Treatment (CA-ARTI-Dx vs. usual care), adjusting for primary symptom (cough, sore throat) and flu season. If the one-sided p-value for the odds ratio of the CA-ARTI-Dx versus usual care is less than or equal to a pre-specified nominal alpha value (e.g. 0.025), the CA-ARTI-Dx will be deemed superior to the control with respect to prescribing of antibiotics. The exact nominal alpha value will be chosen to control one-sided Type I error at approximately 0.025 while accounting for interim analyses.

The second co-primary endpoint (time to return to usual activities) will be analysed with a piecewise exponential time-to-event regression model on treatment (CA-ARTI-Dx vs. usual care), adjusting for primary symptom (cough, sore throat) and flu season. If the upper boundary of the pre-specified 95% (or pre-specified alternative %) confidence interval for the mean difference between treatment arms (CA-ARTI-Dx minus usual care) is less than 1.0 days, the CA-ARTI-Dx will be deemed non-inferior to the control with respect to time to return to usual activities. The percent confidence for the specified confidence interval will be chosen to control one-sided Type I error at approximately 0.025 while accounting for interim analyses.

If a given CA-ARTI-Dx is superior to control on the first co-primary endpoint (antibiotic prescriptions), and non-inferior relative to control on the second co-primary endpoint (time to return to usual activities), the implementation of the CA-ARTI-Dx will be deemed superior to usual care.

